- Table 1-5. Schedule of Activities: Part 3d (AML in United States) Drug-Drug Interaction (DDI) Assessment With Itraconazole was updated to correct an error by including a missing assessment timepoint – pre-dose for day 15 tumor lysis syndrome monitoring test.
- Table 1-6. Schedule of Activities Notes and Abbreviations Definitions was updated to clarify:
 - Neuropathy assessments, as a clinical evaluation, must be performed only for multiple myeloma subjects.

- Timepoints for collection of pharmacokinetic samples for AMG 176 or azacitidine treatment. These timepoints are relative to start of dosing of either AMG 176 or azacitidine.
- A clarification statement was added for the use of core bone marrow biopsy/aspirate performed as standard of care to meet study screening requirements as long as it was performed within 4 weeks from enrollment and no curative anti-cancer therapy was administered during the time from biopsy to enrollment (sections 5.1, 8.1.1, 8.2.2.2.1).
- To maintain consistency, the window to accept previously conducted cardiac imaging tests to meet screening requirement was changed from 30 days of cycle 1 day 1 to 4 weeks of cycle 1 day 1 (Table 1-6 and section 8.2.3.4.2).
- Since Investigator's Brochure was recently updated, the corresponding updates were made into AMG 176 Clinical Experience and Key Benefits (sections 2.2.2.4 and 2.3.2).
- Anti-tumor therapy windows of exclusion criterion 219 were updated to remove reference to "or 5 half-lives, whichever is shorter" from the 14 days and 21 days windows of enrollment (section 5.2).
- Long-term follow up window was increase to \pm 14 days to allow flexibility for these follow up visits. Multiple sections of the protocol were updated to incorporate this change (sections 4.1, 4.4.2, 8.1.5, study schemas, and Table 1-6).
- Azacitidine accountability instructions were updated to clarify that (section 6.1.2.1):
 - Only for intravenous administration of azacitidine, stop date and time is required to be recorded on each subject's case report form.
- Amgen Investigational Product: AMG 176 was updated to (section 6.2.2.1):
 - Clarify dosage adjustments guidelines for AMG 176 by changing the general format of the information.
 - Withholding criteria for elevation of cardiac troponin was modified to elevation > 0.1 ng/mL to emphasize the possibility of allowing subjects to restart AMG 176 treatment even if the elevation is a grade 3.

- Clarify that restarting of AMG 176 dosing can be resumed if deemed safe by the site investigator instead of investigators as previously stated.
- Include updated guidance for collection/report of serious and fatal serious adverse events in alignment to current protocol template (Table 1-6, section 8.2.4.1.4).
- Include a new footnote in Table 11-1 to instruct that for local laboratory tests, all available analytes listed in the table should be recorded in the electronic case report form.
- Remove reference to central testing of troponin-I with high sensitivity Abbott ARCHITECT assay used for exploratory purposes to evaluate biological variations of troponin-I in oncology subjects (section 6.2.2.2.7).
- Administrative and editorial changes (including grammatical, typographical, abbreviations, and formatting) have been made throughout the protocol.

Amendment 15

Protocol Title: A Phase 1 First-in-Human Study Evaluating the Safety, Tolerability, Pharmacokinetics and Pharmacodynamics of AMG 176 in Subjects With Relapsed or Refractory Multiple Myeloma and Subjects With Relapsed or Refractory Acute Myeloid Leukemia

Amgen Protocol Number 20150161

EudraCT Number: 2015-004777-32

NCT Number: NCT02675452

Amendment Date: 09 February 2023

Rationale:

This protocol is being amended for the following reasons:

- The background, rationale, and benefit/risk assessments were substantially revised to include current data and more recent literature.
- Clinical results of the study were updated to reflect the current status of the study as of the most recent data cutoff of 06 September 2022.
- Details about plans for dose optimization to identify the Recommended Phase 2 Dose (RP2D) for the combination of AMG 176 with azacitidine were added, which will be estimated using the totality of data from across the first-in-human (FIH) study, including the pharmacokinetics (PK), safety, efficacy, and other results from the dose escalation and dose expansion.
- Dosing was revised and clarified for Part 5 dose confirmation/optimization (now Part 5a), and an Acute Myeloid Leukemia (AML) conventional dosing schedule was added (Part 5b) along with preclinical data and PK modeling to support investigation of this schedule.
- The dosing language was changed from on 2 consecutive days (QD2) to twice weekly (BIW) to comply with standard and accepted dosing abbreviations.
- Added further language describing that potential drug-drug interactions (DDI) between the study drugs and hormone-based contraceptives are not established. Intrauterine device for contraception methods in females was clarified to non-hormonal (ie, copper) only. The use of oral contraceptives was clarified as

prohibited for the purpose of pregnancy prevention but allowed for the treatment of menorrhagia or other abnormal menstrual bleeding at the discretion of the investigator.

- Number of subjects to be enrolled on the study was updated as follows:
 - Part 3a (closed) enrolled 17 subjects (previously: 15 subjects).
 - Part 3b (closed) enrolled 11 subjects (previously: actively enrolling, with up to 30 subjects planned).
 - Part 3d (open) will enroll up to 11 subjects (previously: up to 8 subjects).
 - Part 4 (open) will enroll approximately 60 subjects (previously: up to 50 subjects).
 - Part 4 Cohort 5 was replaced with Cohorts 5a and 5b, and the figures were updated accordingly.
 - Part 5 (open) will enroll approximately 20 subjects per cohort, approximately 60 subjects in total (previously: up to 20 subjects). It will now consist of Part 5a of 2 cohorts and the new Part 5b (conventional dosing schedule).
 - Enrollment eligibility worksheet and/or subject registration form will be completed and sent to Amgen for verification of eligibility criteria by a site representative.
- Inclusion criteria:
 - 113: Added that for Part 5a cohorts 1 and 2, enrollment will be restricted to subjects with persisting or recurring AML after 1 to 2 lines of prior therapy.
 - 114: For acute myeloid leukemia subjects, blast equivalents are now permissible for greater than or equal to 5% blasts in bone marrow requirement.
- Exclusion criteria:
 - 219, 225, 226, 228, 229: Updated language to clarify chemotherapy, antibody therapy, molecular targeted therapy, investigational agent, strong CYP3A4 inhibitors, CYP3A4 sensitive substrates, own OATP1B1, and/or OATP1B3 or BCRP substrates with a narrow therapeutic window, and any medications are

now disallowed within 5 times the $t_{1/2}$ of the drug, or until the relevant biological effect has resolved (whichever is longer).

- 226: Inhibitors of P-glycoprotein (P-gp) were removed from this exclusion criterion, since preliminary clinical data analysis from the Part 3d and physiologically-based pharmacokinetic (PBPK) modeling and simulation indicated weak to no drug-drug interactions.
- Observed discrepancies between the Schedule of Assessments and the electronic data capture (EDC) were addressed by updating Section 1.3 (Schedule of Activities) of the protocol accordingly. For Part 3d, Part 4, and Part 5a, timepoints of various test procedures (eg, cardiac screening, tumor lysis syndrome tests, echocardiogram, electrocardiogram, [REDACTED] vitals) were revised, and for Part 4 Cohorts 5a and 5b, and Part 5a (AML) Cycle 1 Week 4 procedures were added.
- The reporting period of serious adverse events was updated from “within 24 hours” to “immediately and no later than 24 hours following the investigator’s awareness of the event”.
- The exclusion of azole antifungal therapy was removed since data from Cohort 3d did not identify a DDI between AMG 176 and itraconazole.
- The drug supply information has been updated, to show that AMG 176 will be supplied as a 10 mL liquid deliverable volume in a single-use 20 cc glass vial or a 14.4 mL liquid deliverable volume in a single use 30 cc glass vial (the latter was previously under development).
- The creatinine thresholds for grades 1 through 3 in “Cairo-Bishop Clinical Tumor Lysis Syndrome Definition and Grading” table were corrected (Appendix 8).
- In addition, administrative and editorial changes (including grammatical, typographical, and formatting) have been made throughout the protocol.

Amendment 16

Protocol Title: A Phase 1 First in Human Study Evaluating the Safety, Tolerability, Pharmacokinetics and Pharmacodynamics of AMG 176 in Subjects With Relapsed or Refractory Multiple Myeloma and Subjects With Relapsed or Refractory Acute Myeloid Leukemia

Amgen Protocol Number 20150161

EudraCT Number: 2015-004777-32

NCT Number: NCT02675452

Amendment Date: 13 July 2023

Rationale:

This protocol, dated 13 July 2023, is being amended for the following reasons:

- To clarify that enrollment in Part 5B will start after Part 5A is complete (Section 1.1, Section 4.1, Section 4.1.1) and to provide the dose regimen and number of subjects to be enrolled in both Part 5A and Part 5B (Section 4.1.1, Section 4.4.1 and Section 6.1.2.1).
- To update the Simon's two-stage minimax design for Part 5A to provide interim futility criteria to minimize the number of subjects exposed to a potentially ineffective treatment. The design is based on a two-sided Type I error rate at 0.05 with 0.8 power (Section 1.1, Section 4.1, Section 4.1.1, and Section 9.4.1.1).
- To include omitted pages in Table 1-7 (Schedule of Activities: Part 5B acute myeloid leukemia [AML] Conventional Dosing – Regimen 1) and Table 1-8 (Schedule of Activities: Part 5B [AML] Conventional Dosing – Regimen 2) from amendment 15 to clarify that hospitalization is only required in the first cycle and to indicate the procedures for cycle 2 and beyond. This update allows to monitor safety without overburdening the clinical site and subject with unnecessary procedures.
- Minor updates in the list of references (Section 10).
- In addition, administrative and editorial changes (including grammatical, typographical, and formatting) have been made throughout the protocol.

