
For AML Part 3b and Part 4, each dose cohort will initially enroll 3-4 subjects and up to 10 subjects per cohort may be enrolled. After reviewing all available safety and tolerability data, dose level decisions (eg, escalation/de-escalation/expansion) will be made by the DLRT using a modified Toxicity Probability Interval (mTPI) model (Ji et al, 2010) based on all subjects that have been enrolled at current dose. Dose escalation is considered to be complete if one of the following rules is met:

- The highest planned dose level is evaluated, MTD/MTCD has not been defined and no DLTs occur at any dose level. In this case the maximum administrated dose (MAD) may be used for phase 2.
- An MTD/MTCD is identified.

Guidelines for dose level decisions can be found in [Table 4-2](#). Details regarding the mTPI model and dose finding are described in Section [11.16](#). Please note one exception to the guidelines provided in [Table 4-2](#), a single grade 3 treatment-related troponin elevation will result in dose de-escalation regardless of number of subjects treated at current dose.

Table 4-2. Guidelines for Dose-level Decisions for Part 3b and Part 4

No. of DLT-evaluable ^a subjects treated at current dose	Number of DLTs		
	Escalate	Stay at current dose	De-escalate ^b
3	0	1	≥ 2
6	0-1	-	≥ 2
9	0-1	2	≥ 3
10 ^c	0-1	2-3	≥ 4

DLT = dose-limiting toxicity

^a A subject is considered DLT-evaluable if he/she experienced a DLT during the DLT evaluation period or if he/she received 75% of the planned doses of AMG 176 and completed the DLT evaluation period.

^b De-escalate guideline applies only when current dose level and enrollment is allowed to a lower dose level.

^c The maximum number of evaluable subjects at one dose level is 10.

The MTD/MTCD is defined as the highest dose with a probability of DLT lower than or close to a targeted toxicity probability of 0.2.

For the first dose level and at each new higher dose level, the first enrolled subject will be treated, and then after a period of 72 hours, subsequent subjects will be treated, provided that there are no significant toxicities relating to the treatment of the first subject.

In addition to safety, efficacy of complete remission per ELN in Part 4 will be evaluated. At MTCD or optimal biological dose (OBD), 1 complete remission out of 6 subjects, or 2 complete remissions out of 10 subjects are expected.

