4.3.3 Justification of the Monotherapy Recommended Phase 2 Dose (RP2D)

In the current study, **Part 1** and **Part 2** were initially designed to investigate tapotoclax as monotherapy and combinational therapy in subjects with multiple myeloma (MM). As of December 2019, 48 subjects were enrolled in **Part 1** where clinical responses were observed at dose levels $> 240 \text{ mg/m}^2$. At that time, tapotoclax-associated elevations of troponin were observed at dose levels of 360 mg/m^2 and 480 mg/m^2 . Consequently, to avoid the potential for troponin elevations, only doses less than equal to 240 mg/m^2 are currently under investigation. Additionally, monotherapy efficacy of tapotoclax in AML has been limited, with an overall response rate (ORR = CR + incomplete hematologic recovery [CRI]) of 9.4% (3 out of 32 subjects) in monotherapy **Parts 3a, 3b, and 3c** (all responses were CRI). In contrast, increased antileukemic activity has been observed in combination with azacitidine. Consequently, combination therapy has been prioritized in the current study (**Parts 4 and 5**) to optimize the clinical benefit to subjects, and monotherapy investigations were completed to support the combination therapy studies.

As of November 2022, in AML subjects, 2 out of 17 subjects in **Part 3a** (ORR = 11.8%), 1 out of 11 subjects in **Part 3b** (ORR = 9.1%), 0 out of 4 subjects in **Part 3c** (ORR = 0%), and 3 out of 21 subjects in **Part 4** (ORR = 14.3%) have achieved the best overall response of CR or CRI. With the 21 AML subjects who received combination tapotoclax plus azacitidine in **Part 4**, 12 subjects had at least 1 evaluable disease response; 2 subject (9.6%) had CR; 1 subject (4.8%) had CRI; 8 subjects (38.1%) had stable disease (SD); 1 subject (4.8%) had PD (9 subjects [42.9%] did not have an evaluable disease response) (see [Table 2-1](#) for details). Three out of 21 subjects (14.3%) achieved CRI or better in all cohorts in **Part 4**, and 2 out of 6 subjects (33%) achieved CR in tapotoclax 240 mg/m^2 QW plus azacitidine cohort, demonstrating a better response at the 240 mg/m^2 dose compared with lower doses when administered in combination with azacitidine.

Preliminary PK/PD modeling for tapotoclax (monotherapy or in combination with azacitidine) to date have shown subtherapeutic exposures with regard to the estimated minimum efficacious exposures for tapotoclax at doses below 240 mg/m².

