11.16 Appendix 16. Modified Toxicity Probability Interval Design

A modified Toxicity Probability Interval (mTPI) design will be used to guide dose exploration. The MTD is defined as the highest dose with a probability of DLT lower than or close to a targeted toxicity probability of 0.2. The doses are considered close to the MTD if the toxicity probabilities belong to the proper dosing interval [0.15, 0.25] which corresponds to staying at the current dose (S). The underdosing interval is defined as (0, 0.15) in which the doses are deemed lower than the MTD and corresponds to a dose escalation (E). The overdosing interval is (0.25, 1) in which the doses are deemed higher than the MTD and corresponds to a dose de-escalation (D).

The dose-finding decisions are guided based on Bayesian decision rule by minimizing the posterior expected loss through calculating the unit probability mass (UPM). At each dose level, the UPM is computed for the dosing intervals using the observed data enrolled at current dose. The dose-finding decision is determined as the interval with maximum UPM. A set of independent and non-informative prior Beta (0.5, 0.5) is used for each dose level, which provides equal prior expected loss for the decisions (Ji et al, 2010). Dose escalation will not occur unless at least 6 subjects are treated at the current dose level. In addition, any dose whose posterior probability of toxicity is greater than the target toxicity exceeds 80% will be considered as unacceptable toxicity. This dose and higher doses will not be used again in the trial. Dose exploration will continue until either the maximum number of subjects for Part 3b (n = 11 subjects) and Part 4 (n = approximately 60 subjects) are treated or all doses are determined to be intolerable.

Operating Characteristics

The operating characteristics of the mTPI were evaluated via simulations. The cohort size was fixed to 6 subjects. A total of 3 dose levels were considered for AML Part 3b and 4 dose levels were considered for AML Part 4.

For Part 3b, the design was evaluated for 3 possible dose-response scenarios: Low, Middle, and High MTD. For Part 4, the design was evaluated for 4 possible dose-response scenarios: Low, Middle, and High MTD. [Table 11-5](#) and [Table 11-7](#) show the dose level and true probability of DLT for each scenario used in the simulated studies estimating the MTD. [Table 11-6](#) and [Table 11-8](#) report the operating characteristics from 1 000 simulated studies.

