### 3.3 Adaptive Design

MM Part 1a, Part 1b, and AML Part 3a, **3b**, Part 3c are closed to enrollment.

For AML Part 3b and Part 4, each dose level will initially enroll 3-4 subjects and up to 10 subjects per cohort may be enrolled. A mTPI design will be used to guide dose exploration. The MTD is defined as the highest dose with a probability of DLT lower than or close to a targeted toxicity probability of 0.2. The doses are considered close to the MTD if the toxicity probabilities belong to the proper dosing interval [0.15, 0.25] which corresponds to staying at the current dose (S). The underdosing interval is defined as (0, 0.15) in which the doses are deemed lower than the MTD and corresponds to a dose escalation (E). The overdosing interval is (0.25, 1) in which the doses are deemed higher than the MTD and corresponds to a dose de-escalation (D).

Guidelines for dose level decisions can be found in [Table 2](#). Please note one exception to the guidelines provided in [Table 2](#), a single grade 3 treatment related troponin elevation will result in dose de-escalation regardless of number of subjects treated at current dose.

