**Table 2. Guidelines for Dose-level Decisions for Part 3b and Part 4**

No. of DLT-evaluable a subjects treated at current dose	Number of DLTs		
	Escalate	Stay at current dose	De-escalate b
3	0	1	≥ 2
6	0-1	-	≥ 2
9	0-1	2	≥ 3
10 c	0-1	2-3	≥ 4

DLT = dose-limiting toxicity

a A subject is considered DLT-evaluable if he/she experienced a DLT during the DLT evaluation period or if he/she received 75% of the planned doses of AMG 176 and completed the DLT evaluation period.

b De-escalate guideline applies only when current dose level and enrollment is allowed to a lower dose level.

c The maximum number of evaluable subjects at one dose level is 10.

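### For 0 DLTs in 3 subjects, Protocol Table 4-2 and SAP Table 2 say escalate while Appendix 16 requires 6 subjects first, and nothing says which governs

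*Protocol*

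**What the plan says.** Protocol Section 4.1.1 sets the starting size for Parts 3b and 4: "each dose cohort will initially enroll 3-4 subjects and up to 10 subjects per cohort may be enrolled". Table 4-2 then gives the decision by number of DLTs. Its row for 3 DLT-evaluable subjects reads escalate at 0, stay at 1, de-escalate at 2 or more. The section names one exception to the table: "a single grade 3 treatment-related troponin elevation will result in dose de-escalation regardless of number of subjects treated at current dose". It sends the reader to Section 11.16 for details of the model and the dose finding, without saying that anything there overrides the table.

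Section 11.16 (Appendix 16) does contain a further limit: "Dose escalation will not occur unless at least 6 subjects are treated at the current dose level". It also has an excess-toxicity rule: "any dose whose posterior probability of toxicity is greater than the target toxicity exceeds 80% will be considered as unacceptable toxicity". Of the simulations behind Tables 11-6 and 11-8 it says: "The cohort size was fixed to 6 subjects".

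SAP Section 3.3 repeats the starting size ("each dose level will initially enroll 3-4 subjects and up to 10 subjects per cohort may be enrolled"), the dosing intervals and the troponin exception. It reproduces the same grid as "Table 2. Guidelines for Dose-level Decisions for Part 3b and Part 4", with the same row for 3 subjects. It does not mention a 6-subject minimum.

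**The concern.** Cohorts start at 3 or 4 subjects, so with 3 evaluable the 0/3 cell is the first decision a dose can reach. At that point one text permits a higher dose to open and another forbids it until the number treated has doubled. The dose-level review team is given the table as its guide, and the table discloses one exception but not this one.

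The cell is not a remote case. Protocol Section 2.1 reports no DLTs in the 33 subjects enrolled in Parts 3b and 4 as of November 2022, so any escalation in that period with 3 evaluable subjects would have used exactly this cell. At stake are how much safety information stands behind each step up in dose, and whether the final report can say which rule the trial followed.

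**Working it through.** **Inputs (Appendix 16).** Target 0.2; intervals (0, 0.15), [0.15, 0.25], (0.25, 1); prior Beta(0.5, 0.5); a dose is unacceptable if P(p > 0.2 given the data) exceeds 0.80. With x DLTs in n subjects the posterior is Beta(0.5 + x, 0.5 + n − x). The unit probability mass (UPM) is posterior mass divided by interval length, and the decision is the interval with the largest UPM.

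**Step 1: reproduce the table.**

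| DLTs/n | UPM escalate / stay / de-escalate | P(p > 0.2) | UPM alone | Table |
|---|---|---|---|---|
| 0/3 | 4.65 / 1.33 / 0.23 | – | Escalate | Escalate |
| 1/6 | 2.66 / 2.53 / 0.46 | 0.465 | Escalate | Escalate |
| 2/6 | 0.73 / 1.88 / 0.94 | 0.804 | Stay | De-escalate |
| 3/9 | 0.48 / 1.96 / 0.98 | 0.844 | Stay | De-escalate |
| 3/10 | 0.66 / 2.39 / 0.88 | 0.795 | Stay | Stay |

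The remaining cells also reproduce. The 2/6 and 3/9 entries can be obtained only by applying the 80% rule. So the table already contains one Appendix 16 safety rule and leaves out the other.

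**Step 2: size of the difference.** Take the chance of escalating past a dose on the first visit to it, with true DLT rate p, q = 1 − p and all subjects DLT-evaluable.

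- Table, 3-subject start (0/3, or 1/3 then 0 of the next 3): q³ + 3pq²·q³.
- Table, 4-subject start (0/4, or 1/4 then 0 of the next 2): q⁴ + 4pq³·q². The tables have no row for 4, so the model output is used: 0/4 has UPM 5.07 / 1.22 / 0.16 (escalate) and 1/4 has 1.67 / 2.07 / 0.72 (stay).
- 6-subject minimum (at most 1 in 6): q⁶ + 6pq⁵.

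At p = 0.20 these are 0.512 + 0.384 × 0.512 = 0.709; 0.4096 + 0.4096 × 0.64 = 0.672; and 0.262 + 0.393 = 0.655.

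| p | Table, start 3 | Table, start 4 | 6-subject minimum | Difference in points (start 3; start 4) |
|---|---|---|---|---|
| 0.20 | 70.9% | 67.2% | 65.5% | 5.3; 1.6 |
| 0.30 | 49.4% | 44.2% | 42.0% | 7.4; 2.2 |
| 0.40 | 30.9% | 25.4% | 23.3% | 7.6; 2.1 |

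The chance of escalating on 3 subjects alone is q³: 51.2%, 34.3% and 21.6%. Under Appendix 16 it is zero.

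**Step 3: does the minimum fit Part 3b?** Reaching the third dose needs at least 6 + 6 + 1 = 13 newly enrolled subjects. Appendix 16 gives a maximum of 11, and Part 3b closed at 11 over three doses.

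**Step 4: do the simulations describe either rule?** They used 6-subject cohorts. However, Table 11-6 has a median of 20 subjects in every scenario, against the stated 11 for Part 3b. Table 11-8 has a median of 50 in the Middle and High scenarios over 4 doses, while the cap of 10 evaluable subjects per dose allows 4 × 10 = 40.

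**Step 5: counts in Part 4.** Protocol Section 4.3.3 gives the November 2022 total ("With the 21 AML subjects who received combination tapotoclax plus azacitidine in" Part 4) and 6 subjects at 240 mg/m² QW. At most 21 − 6 = 15 remain for 60, 120 and 180 mg/m² QW, or 22 − 6 = 16 with the enrolled count in Section 2.1. A 6-subject minimum at three doses needs 18.

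**The case against.** The best reply is that the table is headed as guidelines, the review team decides on all available data, and Appendix 16 is worded as a bar, so it simply limits the table. The mandatory wording is a good reason to prefer the minimum. But no text says that it prevails, the section that introduces the table names only the troponin exception, and under this reading the escalate entry in the 3-subject row could hardly ever be used. Since the table already carries the 80% rule, a user has no cause to expect a second Appendix 16 limit outside it. The different denominators (treated in Appendix 16, DLT-evaluable in the tables) do not remove the conflict when a cohort opens with 3 or 4 subjects.

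It is also fair that the effect is modest, that no DLTs had been seen as of November 2022, that Part 3b is closed, and that SAP Section 10 reports early termination. This limits the size of the point and moves much of the remedy to the report.

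Two stronger readings are tempting, and the documents do not support them.

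- *Doses were escalated before 6 subjects.* The 15 or 16 against 18 points that way, but only indirectly. Section 4.1.1 lets subjects cross over into Part 4 and keeps their DLTs out of dose-level decisions, without saying whether they count as treated. The counts predate the July 2023 amendment, and the Appendix 16 text then in force is not available. Table 2-1 cannot settle it: its Part 3b monotherapy columns sum to 5 + 5 + 4 = 14 against 11 enrolled, and one azacitidine column is labelled Part 3b.
- *The simulations fit once the 6-subject rule governs, so only the table is wrong.* Step 4 shows that they do not.

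**Conclusion.** The inconsistency is real and concerns a safety threshold: at 0 DLTs in 3 subjects the two rules give opposite instructions, and neither document resolves them. It is confined to the escalate decision below 6 subjects. It is worth fixing but modest in size: about 5 to 8 points per dose with a 3-subject start and about 2 with a 4-subject start. Those figures assume true DLT rates of 0.20 to 0.40, independent subjects who are all DLT-evaluable, and no troponin-triggered de-escalation. They describe passage past a single dose. They do not show a bias in the maximum tolerated combination dose, and none is claimed. Whether the 3-subject row was ever used cannot be determined from the documents.

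**What to change.** For Part 4, let the 6-subject minimum govern, because it is the mandatory and safer rule. Replace *escalate* at 0/3 with *enrol to 6* in Protocol Table 4-2 and SAP Table 2. List the minimum beside the troponin exception in Protocol Section 4.1.1 and SAP Section 3.3, and say whether the 6 are treated or DLT-evaluable.

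Do not impose the rule retrospectively on Part 3b, whose 11 subjects could not satisfy it with new enrolment alone. For both parts, state in the synopsis CSR which rule supported each escalation and how many DLT-evaluable subjects there were at that point. State there too that Tables 11-6 and 11-8 do not match the current design under either rule.

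The cost is one table cell and a sentence or two in each document, plus a short statement in the CSR. No extra subjects are needed, and describing the simulations accurately does not require rerunning them.

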5	AML (approximately 68 subjects [24 per cohort in Part 5A, 20 in Part 5B])	Part 5A: AMG 176 in combination with azacitidine  Cohorts 1 and 2: OBD Selection (QW or BIW). Part 5B: Conventional AML Dosing Schedule (5 consecutive days)	Part 5 will begin after the completion of Part 4. Part 5A: 

Two cohorts will be enrolled to determine the combination RP2D/OBD on either a QW or BIW dosing schedule.

Simon's two-stage minimax design (Simon, 1989) will be used in each cohort of Part 5A for conducting the trial.

Enrollment will be restricted to subjects with persisting or recurring AML <math>\leq</math> 2 prior lines of therapy.

 Part 5B (The enrollment of Part 5B will start after Part 5A is complete): 

Two regimens will be tested, both continuing to utilize a 28-day cycle.

All subjects will receive 7 days of azacitidine IV or SC daily at 75 mg/m^2 on Days 1 - 5, 8 - 9 of each 28-day cycle.

Regimen 1 will administer AMG 176 at 240 mg/m^2 QD for 3 days + 4 days off followed by BIW dosing on weeks 2 and 3.

Regimen 2 will administer AMG 176 at 240 mg/m^2 QD for 5 consecutive days, and then BIW on week 2 (no administration on weeks 3 and 4). Regimen 2 will only enroll if no safety issues arise after 6 subjects have enrolled in Regimen 1.

Doses other than the stated 240 mg/m^2 based on emerging data.

AML = acute myeloid leukemia; BIW = twice weekly; DLRT = dose-level review team; IV = intravenous;

MM = multiple myeloma; MTD = maximum tolerated dose; mTPI = modified toxicity probability interval;

PD = pharmacodynamics; PK = pharmacokinetics; QD = once daily; QW = once weekly;

[figure not shown]
RP2D = recommended phase 2 dose; SC = subcutaneous; US = United States

Note: Part 2 was designed to be a combination treatment for MM in a previous amendment. It was removed due to a change in AMG 176 clinical development.

In this study, Part 1 and Part 2 were initially designed to investigate AMG 176 as monotherapy and combinational therapy in subjects with multiple myeloma (MM). As of December 2019, 48 subjects were enrolled in Part 1 where clinical responses were

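### Section 4.1.1 and Appendix 16 of the protocol end Part 4 dose finding by different rules, and the Appendix 16 end points will often not be reached under the cap of 10 evaluable subjects per level

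*Protocol*

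**What the plan says.** Protocol Section 4.1.1, on Parts 3b and 4, introduces its end rule with "Dose escalation is considered to be complete if one of the following rules is met". The first rule is "The highest planned dose level is evaluated, MTD/MTCD has not been defined and no DLTs occur at any dose level"; the second is "An MTD/MTCD is identified". The section then refers to Section 11.16 (Appendix 16) for the mTPI model and dose finding.

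Appendix 16 gives its own end rule, which opens "Dose exploration will continue until either the maximum number of subjects for Part 3b (n = 11 subjects) and Part 4". It puts the Part 4 number at about 60, and the only other way to stop is for every dose to be found intolerable. It also requires at least 6 subjects at a level before escalation, and it permanently closes a dose, and all higher doses, once the posterior probability that toxicity exceeds the target is above 80%.

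The cap is in footnote c of protocol Table 4-2 and SAP Table 2: "The maximum number of evaluable subjects at one dose level is 10". The body of Section 4.1.1 also limits enrollment to 10 per cohort. Protocol Table 4-1 lists six Part 4 cohorts: four QW (60, 120, 180 and 240 mg/m²) and two BIW (120 and 240 mg/m²). SAP 3.3 repeats the mTPI intervals, decision table and cap but gives no completion rule.

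**The concern.** The two end rules for one design share no condition. When an MTCD has been identified, Section 4.1.1 says that escalation is complete, while Appendix 16 says to go on. The same holds when the top dose is cleared without DLTs.

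The Appendix 16 rule also fits poorly with the cap. Its target of about 60 generally needs every planned cohort to be full, yet the escalation rules move on after 6 subjects and close toxic doses for good. At 10 subjects with 2 or 3 DLTs, Table 4-2 says to stay at the dose, but no places remain there.

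At stake are when Part 4 counts as finished and how many subjects enter levels on which the model has already decided. SAP 3.1 says "Part 5 will begin after the completion of Part 4", so the end of Part 4 bears on the opening of the expansion. The printed operating characteristics are also meant to show how the design behaves, which they can do only if they follow the rules in force.

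**Working it through.** **Inputs.** Four QW and two BIW cohorts (Table 4-1); at most 10 evaluable subjects per level (Table 4-2, footnote c); Beta(0.5, 0.5) prior, intervals cut at 0.15 and 0.25, closure if P(p > 0.2) > 0.80, and 6 subjects before escalation (Appendix 16); true DLT rates from Table 11-7; printed results from Table 11-8.

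**1. The plan's own figures.** (4 + 2) × 10 = 60, which matches the Part 4 number. With the prior and intervals above, choosing the interval with the largest unit probability mass and then applying the 80% closure reproduces every cell of Table 4-2. For example, 2 DLTs in 6 gives P(p > 0.2) = 0.804, so the dose closes.

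**2. Ceiling under a strict cap.** Let a ladder have L levels, and let level *j* close after *c* subjects, before any higher level is used. If every other place is filled, the most that Part 4 can treat is 60 − (10 − c) − 10 × (L − j).

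| Level closed | c | Ceiling |
|---|---|---|
| Top of either ladder | 3 | 53 |
| Top of either ladder | 6 | 56 |
| Top of either ladder | 8, 9, 10 | 58, 59, 60 |
| One below the top | 3 | 43 |
| One below the top | 6 | 46 |
| Lowest QW level | 6 | 26 |

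**3. No closure and no DLTs.** Escalating after 6 per cohort and filling only the top cohort of each ladder gives (6 + 6 + 6 + 10) + (6 + 10) = 44. Neither Appendix 16 end point is met, so the gap does not depend on a dose being closed.

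**4. Simulation of the QW ladder with the cap.** Subjects enter six at a time, then up to 10 per level. A trial ends without an Appendix 16 end point when the rules point to a level with no places left.

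| Scenario | All four QW levels closed | Neither end point | No level closed |
|---|---|---|---|
| Low | about 35% | about 65% | 1 − 0.991 = about 1% |
| Middle | 11% to 12% | about 88% (88% to 89% over repeat runs) | 1 − 0.774 = about 23% |
| High | about 3% | about 97% | 1 − 0.568 = about 43% |

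Four levels at 10 hold at most 40, so this ladder cannot reach 60 alone; the middle column is in effect the share in which not all QW levels close. The useful question is therefore whether the QW ladder supplies its 40. Median QW numbers were 16, 22 and 28, and upper quartiles were 22, 28 and 28. Even with both BIW cohorts full (+20), the medians become 36, 42 and 48 and the upper quartiles 42, 48 and 48, all well short of about 60.

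**5. Table 11-8.** It reports a median of 50 subjects in Middle and High on four dose levels, but 4 × 10 = 40. Rerunning without the cap to a maximum of 50 gives a median of 50 in both. In Low, the rerun finds all doses intolerable in 47.5% of trials. The printed selection percentages leave 100 − (42.7 + 9.29 + 0.47 + 0.03) = 47.51% with no dose selected. The printed Low median of 36 was not reproduced (50 in the rerun).

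**The case against.** The best defense separates two ideas: escalation being complete ends upward moves, while exploration covers continued enrollment up to a maximum. The dose-level review team may also expand, repeat or terminate cohorts, and Appendix 3 lets enrollment to a cohort stop at any time. This discretion is real, and cohorts could be filled toward 60 by choice. It does not reconcile the texts, because the protocol labels Part 4 as a whole dose exploration (Figure 1-8) and Section 4.1.1 defers to Appendix 16 for the same dose finding.

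Several stronger inferences are tempting, and the documents do not support them:

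- **That neither end point can occur once one dose is closed and another is open.** A top dose can close at 4 DLTs in 10 (P(p > 0.2) = 0.934) with 60 still reachable. Ceilings of 58 or 59 are approximately 60. The footnote caps evaluable subjects, and Section 4.2.1 replaces those who are not evaluable. Figure 1-8 allows added cohorts. The remaining doses may also close later.
- **That Section 4.1.1 is met at 36 subjects, so Appendix 16 costs 24 more.** The 36 (6 × 6) borrows the six-subject minimum, which stands only in Appendix 16; Table 4-2 allows escalation at 0 DLTs in 3.
- **That the printed Part 4 simulations mostly run to the maximum.** In Low, the median is 36 with an interquartile range of 6 to 50.
- **That the Appendix 16 rule alone controls the start of Part 5.** Table 4-1 ties that start to determining the combination RP2D.

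It is also fair that SAP 3.3 contradicts nothing, since it has no completion rule, and that SAP Section 10 records early termination. Rewording therefore cannot now change enrollment. It can still make clear which rule governed the data.

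**Conclusion.** The point holds as an inconsistency in a stated decision rule. Section 4.1.1 and Appendix 16 end the same design differently, and this is visible without calculation. With six planned cohorts and 10 evaluable subjects per level, the Appendix 16 end points will often not be reached, whether or not a dose has been closed: about 65%, 88% and 97% of Low, Middle and High trials on the QW ladder.

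Those shares assume a strict cap, rule-driven enrollment with no added cohorts or discretionary filling, and the plan's own toxicity scenarios. They cover the QW ladder only. The step that adds 20 BIW subjects is a generous bound, not a simulation.

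Separately, Table 11-8 cannot describe the capped design, since a median of 50 exceeds the 40 that four levels allow. The pattern fits an uncapped simulation to a maximum of 50, apart from the unreproduced Low median.

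**What to change.** Reconcile the two passages. One completion rule, chosen by the sponsor, should stand in Section 4.1.1 and Appendix 16 and be carried into SAP 3.3, with a statement of how it applies to the QW and BIW cohorts. The text should say whether about 60 is a ceiling on Part 4 or a condition for continuing. This review does not propose the content of the rule.

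For Table 11-8, either rerun the simulation with the cap and the chosen rule, or add a note that it was simulated without the cap to a maximum of 50, if the sponsor's records confirm that.

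Because the study was terminated early, the clinical study report should state which rule was applied in Part 4 and on what basis dose finding ended.

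The cost is wording in three places, one short simulation or a table note, and a sentence in the report. No subjects are added.
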